Phase I Assessments. Given that the primary purpose of Phase I is to efficiently induce weight loss for Phase II, assessments will be minimal. Pre- and post-treatment assessments will be relatively minimal, taking approximately 45-minutes to complete. The following will be collected:

Demographics. Demographics (e.g., sex [male, female, non-binary], age, income) will be collected at pretreatment only.

Weight and height. At both pre- and post-treatment, weight will be measured to the nearest 0.1kg using a digital scale. Height will be measured to the nearest millimeter using a stadiometer (baseline only). Participants will be measured wearing light, indoor clothing without shoes.

Maintenance treatment mechanisms. While Phase I processes of change are not the focus of the study, we will include pre-post tests of delayed discounting^{60,61} (see phase II measures) and PA. Accelerometry will be used in Phase II (focus of study) but not in Phase I for cost and efficiency reasons. Instead, the **Paffenbarger Activity Questionnaire (PAQ)**^{62,63}, will assess the hours/day an individual spends doing various levels of physical activity in a typical weekday and weekend day. The PAQ is frequently used in the field and has been found to have good validity and reliability among adults.

Financial literacy will also be assessed at baseline to clarify any role that financial literacy may play in Delay Discounting scores⁹⁶.

We will also ask participants to tell us their mobile phone service provider. Our Phase II treatment website will need to be adapted slightly for rare service providers that we have not yet come across, so we need to determine if we need to make these adaptions during Phase I of the program.

PHASE II APPROACH

Participants. Those who lose at least 5% of initial body weight during Phase I (N=70) will be eligible to participate in Phase II, the weight loss maintenance trial (i.e. the primary focus of the application). Given our previous findings^{44,52,53,59}, we anticipate that the demographic characteristics of participants entering Phase II will be similar to those of participants in Phase I. In addition, in a previous trial in which we used the proposed two phase maintenance design with Phase I as the Web program, we found that 99% of participants who met the 5% weight loss criterion in Phase I elected to continue into Phase II⁴⁴.

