Physical Activity (Primary Outcome). The validated^{83,84} Actigraph GT9X will be worn on the waist for 7-days at Phase II 0,1, 2, and 4 months. Data will be processed with the ActiLife software, ensuring wear time requirements and validated algorithms. Time spent in MVPA and bout-related MVPA (≥ 10 min in duration) will be examined. In addition, following [name] et al.’s protocol that has been validated against accelerometry^{75,77}, each EMA prompt will include questions about activity type and purpose that cannot be captured by accelerometers. To allow for future direct comparisons of Phase I processes, we will also administer the Paffenbarger (PAQ)^{62,63}.

Weight (Secondary Outcome). Weight will be measured to the nearest 0.1kg with a digital scale. Participants will be measured wearing one layer of clothing without shoes. Weight will also be measured objectively at each WLM session and reported over the phone to case-managers on a weekly basis.

Environmental Context (Moderators). EMA measures of the environment focus on factors that may alter the cost/benefits of PA. On each EMA prompt, participants will be asked to indicate their current physical and social context. Following Elliston et al.²⁴, participants will be asked whether they can see others in their environment being physically active (**norms**), whether a TV or computer can be seen from where they are sitting/standing (**sedentary options**), and whether exercise equipment is available or if they are within a 5- minute walk to a place they can be physically active (**accessibility**). We will then ask, consistent with Booker & Mullan⁸⁵, about 5 potential PA triggers (physical, sensory, social, internal, and external drives; e.g., “Right now, are there any social triggers in the environment which are influencing your physical activity”). The mean of the 5 items will be used to create an **environmental responsiveness** score. Consistent with other EMA protocols⁸⁶, **stress** will be assessed with 3-items of the Perceived Stress Scale⁸⁷ adapted for momentary use (e.g., “How stressed do you feel right now”) and **social support** will be measured with 1-item⁸⁸. Local **weather** indices will be obtained for the EMA dates from a national weather service, as we have done in a prior study⁸⁹.

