Power. Based on prior DD and EFT work^{31,34,39}, power is computed for an effect size (d) of 0.50. The computations assume an intraclass correlation (ICC) of 0.250 for the 4 time points clustered within each participant. The standard deviation is assumed to be the same in the two conditions. The criterion for significance (alpha) has been set at 0.05. The test is 2-tailed, which means that an effect in either direction will be interpreted. Given these assumptions, the study will have 82.1% power to yield a statistically significant result that will increase in one unit per number of individual covariate(s) included in the models. Accounting for 15% attrition, 15 more participants will be added, so a total of 160 participants will be enrolled in Phase I.

Analyses.

Primary hypothesis 1: WLM+FT will produce more engagement of DD and PA adherence. Descriptive statistics will be generated on all the demographic variables as well as mediators (DD), moderators

(environmental variables), covariates (WAIS-II) and outcomes (PA and weight). Differences between WLM-HT and WLM+FT will be assessed through chi-square tests (proportions) or Student's t-test (means) at each time point; if differences on any of the demographics are found at baseline, the variable will be used as a covariate in the main model. The main outcome, PA distribution data will be examined and if variables violate distributional assumptions of normality, will be analyzed using generalized linear model (GLM) procedures, which enable the use of non-Gaussian error models. Using a mixed-effects model in Mplus we will be able to estimate the main effect of the intervention considering the four time points nested within individuals allowing for time-varying effects of covariates to vary with time for the daily data collected.

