Primary hypothesis 2: Within-person mediational pathways will be found between participation in the intervention and PA and changes in DD on 2a) a daily basis (EMA) and 2b) over longer-time periods (1- and 2month change predicting PA outcomes at 4 months). Using mixed-effects mediation modeling assuming time points clustered within individuals with Mplus and mediation package from R[104-107], we will test how the relationship between intervention condition and PA is mediated by change in DD over time by using daily data and also running prediction models by the four time points. DD will be evaluated for normality and linearity assumptions and if assumptions are violated, GLM models will be established to determine the indirect effect.

Exploratory hypothesis: Environmental context will moderate the mediational pathways such that DD will be a stronger determinant of behavior in environments with more proximal costs. A moderated mediation mixedeffects model will test the strength or weakness of the indirect effect and/or the direct effect of the intervention condition on PA by the different environmental factors measured. The mixed-effects will consider effects by the daily data collected within the four general time points nested within individuals.

Missing data. We will run a systematic analysis of missing EMA data to determine whether the likelihood of response at any given prompt is time-varying (e.g., time of day/week, activity level). We anticipate approximately ~80% of prompts will be answered⁷⁵. If needed, we will use multilevel data imputation strategies ⁹⁴. For clinicbased data, type of missingness will be evaluated and values will be imputed using full information or restricted maximum likelihood estimation ⁹⁵. All variables in our models will be used to impute missing data. Sensitivity analyses will be used to compare results with and without imputed values.

Inclusion/Exclusion Criteria.

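### Self-reported activity (PAQ) is collected before randomisation and again in Phase II but has no role in the primary physical activity analysis; pre-specifying it is a cheap, modest gain in precision

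*Combined protocol and SAP*

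**What the plan says.** **Outcome.** Under Physical Activity (Primary Outcome), the accelerometer is worn for 7 days at Phase II months 0, 1, 2 and 4. The statement of hypotheses in the introduction measures PA adherence by EMA and accelerometry.

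**PAQ.** Phase I Assessments uses the PAQ before and after treatment in place of the accelerometer. It "will assess the hours/day an individual spends doing various levels of physical activity in a typical weekday and weekend day". In Phase II it is given again: "To allow for future direct comparisons of Phase I processes, we will also administer the Paffenbarger (PAQ"). No Phase II visits are listed for it.

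**Analysis.** The hypothesis 1 model is a mixed model on the four time points. The covariates mentioned are an intelligence measure and any demographic found to differ between arms at baseline. For missing data, clinic-based values are handled by full-information or restricted maximum likelihood, and "All variables in our models will be used to impute missing data". The PAQ appears in none of these statements.

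**Power.** "power is computed for an effect size (d) of 0.50", with "The computations assume an intraclass correlation (ICC) of 0.250 for the 4 time points clustered within each participant". The effect size is justified from delay discounting and episodic future thinking studies.

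**The concern.** About 60 participants are expected to be analysed, so precision is scarce. If the plan's ICC of 0.25 describes accelerometer weeks, one baseline week correlates only √0.25 = 0.5 with a person's stable activity level. A second pre-randomisation measure that asks about typical days could then carry information that the baseline week misses.

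An accelerometer week can also fail its wear-time requirement although the questionnaire is complete: Data management says survey links go out 48 hours before the visit. In that case an activity measure already in hand would go unused when the missing week is handled.

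At stake is a somewhat wider confidence interval for the primary PA comparison than the collected data require. There is also some room for a data-driven choice of covariates later, because the PAQ has no pre-specified role.

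**Working it through.** **Inputs from the documents**
- d = 0.50, ICC ρ = 0.25 and 4 time points; also "The criterion for significance (alpha) has been set at 0.05" and "The test is 2-tailed" (Power).
- 70 randomised (Overview) and 15% attrition (Power): 70 × 0.85 = 59.5, or about 30 per arm.

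**Assumptions, not in the documents**
- 1:1 allocation, equal correlation between any two visits, and a constant effect over the visits averaged.
- c, the correlation of the PAQ with one accelerometer week, taken as 0.1 to 0.3.

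**Step 1: reproduce the plan.** On a scale where one visit has SD 1, the mean of four visits has variance (1 + 3 × 0.25)/4 = 0.4375. The standard error of the difference is √(2 × 0.4375/30) = 0.1708, and the noncentrality is 0.50/0.1708 = 2.93. The noncentral t gives 82.1%, which matches "the study will have 82.1% power to yield a statistically significant result". With all 35 per arm the figure is 87.6%, so the stated power appears to be after attrition.

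**Step 2: baseline-adjusted comparison.** The mean of the three post-baseline weeks has variance (1 + 2 × 0.25)/3 = 0.50. Adjusting for the month-0 accelerometer removes 0.25² = 0.0625 and leaves 0.4375. Power is again 82.1%; the equality with step 1 is a coincidence at this ICC. This is the reference for what follows, so credit for the baseline accelerometer is already taken.

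**Step 3: add one pre-randomisation PAQ.** If it correlates c with every accelerometer week, it removes a further [c(1 − ρ)]²/(1 − c²). For c = 0.3 and ρ = 0.25 this is 0.225²/0.91 = 0.0556, which leaves 0.3819. One more degree of freedom is spent.

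| c | Variance, ICC 0.25 | Power | Gain (points) | Gain at ICC 0.5 |
|---|---|---|---|---|
| none | 0.4375 | 82.1% | – | – |
| 0.1 | 0.4318 | 82.5% | 0.5 | 0.2 |
| 0.2 | 0.4141 | 84.1% | 2.0 | 0.9 |
| 0.3 | 0.3819 | 86.9% | 4.8 | 2.1 |

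At ICC 0.5 the reference variance is 2/3 − 0.25 = 0.4167 (power 83.9%). With 35 per arm and ICC 0.25, the gains are 0.4, 1.7 and 3.9 points.

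**Step 4: PAQ weaker for later weeks.** If it correlates c₀ with the month-0 week and c₁ with later weeks, it removes (c₁ − ρc₀)²/(1 − c₀²). With ρ = 0.25:
- c₀ = 0.3, c₁ = 0.2: (0.2 − 0.075)²/0.91 = 0.0172, a gain of 1.5 points.
- c₀ = 0.4, c₁ = 0.25: (0.25 − 0.1)²/0.84 = 0.0268, a gain of 2.3 points.

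**Step 5: how demanding is c = 0.3?** At ICC 0.25 it implies that the PAQ correlates 0.3/0.5 = 0.6 with stable activity. That makes 0.3 a favourable value, not a cautious one.

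**The case against.** The strongest reply is that this is a preference and not a defect. The PAQ has a stated purpose, the objective month-0 accelerometer value is already among the four modelled time points, and omitting an optional self-report covariate from a randomised comparison causes no bias and contradicts nothing. That stands, and it limits the point to an efficiency suggestion.

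Four more specific objections also stand:
- The ICC is given for four time points in a power paragraph built on discounting studies. It is not stated to describe accelerometer weeks.
- No Phase II PAQ visits are listed, so a month-0 PAQ or one at the same visit as the accelerometer cannot be taken for granted. The Phase I post-treatment PAQ can.
- A questionnaire about typical days is not the best record of one particular week. EMA asks about activity over 7 days at months 0, 2 and 4, and the protocol describes those items as validated against accelerometry. At month 1 there is no EMA.
- The missing-data sentence says that model variables will be used; it does not say that nothing else may be. A missed visit may also lose the PAQ together with the accelerometer, and no rate of lost weeks is given.

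None of this removes the basic observation: a pre-randomisation measure of the same construct as the primary outcome is collected and given no analytic role.

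**Conclusion.** The point holds as a small, inexpensive gain in precision. At the plan's ICC one PAQ is worth about 0.5 to 4.8 power points over assumed correlations of 0.1 to 0.3. The gain is 0.2 to 2.1 points if the ICC is 0.5, and smaller if the PAQ tracks later weeks less well than the baseline week. These figures rest on the assumptions listed above and on d = 0.50 being relevant to PA. The missing-data benefit is plausible in direction only.

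A reader might infer that a gain of 5 to 6 points follows from the plan's own ICC. It does not. The ICC says nothing about how the PAQ relates to the accelerometer, and one PAQ falls short of 5 points even at a correlation of 0.3. A reader might also infer that the primary analysis is biased or underpowered without the PAQ. The documents do not support that either: the stated 82.1% reproduces without it.

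**What to change.** Add two sentences to the analysis plan.

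1. In the hypothesis 1 model for accelerometer PA, include the Phase I post-treatment PAQ as a covariate beside the month-0 accelerometer value, whether or not the arms differ at baseline. If a Phase II month-0 PAQ is taken before randomisation, use the mean of the two.
2. In the likelihood-based handling of missing accelerometer weeks, name any post-randomisation PAQ and the EMA activity items as auxiliary variables. They are never covariates, since treatment may affect them.

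The plan should also list the Phase II visits at which the PAQ is given. If they match the visits already intended, no new data are needed. The cost is one degree of freedom, with no gain if the PAQ proves unrelated to accelerometer activity.

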Additional Temporal Self-Regulation Theory Measures. To test the full TST model, we will supplement EMA with clinic-based assessments of intentions⁷², habits⁹⁰, and temporal contingency^{15,91}. The following validated environment measures will also be administered: Weight Related Social Norms⁹² adapted for PA, Exercise Environment Questionnaire¹³ and a survey on sedentary activity options¹⁴ (accessibility; sedentary options), Environmental responsiveness²³, Perceived Stress Scale⁸⁷, and the Social Support and Exercise Survey⁹³, Physical Activity Enjoyment Scale⁹⁹, Behavioral Regulation of Exercise Questionnaire¹⁰⁰, Self-efficacy for exercise¹⁰¹, CHAOS¹⁰¹, and the Three Factor Eating Questionnaire- 18¹⁰². These measures are reliable and sensitive to obesity or eating behaviors, and for EF.

Additionally, frequency of self-weighing will be assessed in phase II assessments as it has been found to be a predictor of weight maintenance¹⁰⁴.

Treatment acceptability will be measured using a questionnaire adapted from prior weight control and EFT studies⁵¹.

Phase II Summary of Time Commitment

9 in-person treatment sessions (7 groups, 2 case-management) over the course of 4 months, each 30-90 minutes in duration

Approximately 14 phone calls (about 15 minutes each) with a case manager, on weeks when there is not an in-person case management session.

4 assessments are completed in our office at 0 (90 min), 1 (30 min), 2 (60 min) and 4 months (60 min).

Accelerometry data is collected for 7 days at 0, 1, 2, and 4 months.

EMA will be conducted for 7 days at 0, 2, and 4 months.

Phase I & II contingency plan for assessment procedures during national emergencies such as COVID-19.

Because assessments take place in person, alternative remote procedures will be implemented in the case that in-person contact poses a health risk to participants. In these cases, data will be collected using the following methods:

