Weight. Weights may be collected using a digital scale that will securely transmit participant weights back to study staff via cell tower. Given that these e-scales are expensive and could be cost-prohibitive, weights may also be collected by sending a bathroom scale to participants and having participants complete a remote assessment visit via videoconference. During the videoconference, research staff will guide participants through a remote assessment to ensure that they follow all gold-standard weigh-in assessment procedures (e.g., one layer of clothing, no shoes, empty pockets, etc.). Calibration weights will also be included with the scale, and participants will be asked to validate the scale’s accuracy before weighing themselves. Participants will show the scale’s read-out to research staff via the videoconference function. Participants will return the scale to the lab (the scale is not

an incentive/honorarium). Weight may also be collected via participant self-report. In these instances, participants will be asked to step on their home scale and to take a picture of their current weight. They will then email this picture to the study staff as a record of their assessment weight.

Adverse Event Interviews. The occurrence of adverse events will be assessed via Qualtrics, email or phone instead of in person.

Compensation. In case of national emergency, participants will receive e-gift cards, checks, money orders, or other electronic payment (e.g., PayPal) with a value based on the assessment time period. That is, they will not receive any extra compensation for these procedures. Instead, they will receive their typical compensation, just via electronic or mail delivery method (as opposed to receiving cash in-person) to help ensure safety during COVID-19.

Quality control.

Data management.

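### In an emergency, an unsupervised photo of an uncalibrated home scale can serve as the assessment weight, with no same-scale rule, so a change of scale can enter the 5% gate, the weight-loss stratum and Phase II weight change.

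*Combined protocol and SAP*

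**What the plan says.** By default, Phase I weights are taken the same way at both ends: "At both pre- and post-treatment, weight will be measured to the nearest 0.1kg using a digital scale" (Phase I Assessments, Weight and height). The remote alternatives come under the heading "Phase I & II contingency plan for assessment procedures during national emergencies such as COVID-19", so they reach the Phase I weights as well as the Phase II ones. The Weight paragraph there lists three:

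- **E-scale:** a digital scale that transmits readings to staff.
- **Mailed bathroom scale:** staff guide the weigh-in by video, and "Calibration weights will also be included with the scale". The scale goes back to the lab afterwards.
- **Participant's own scale:** "Weight may also be collected via participant self-report. In these instances, participants will be asked to step on their home scale", with a photo of the reading. On its status the plan says: "They will then email this picture to the study staff as a record of their assessment weight".

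Calibration and staff guidance are stated only for the mailed scale. The paragraph does not rank the methods, require one method at both ends, exclude the photo from the eligibility weight, or ask for the method to be recorded. The Analyses and Missing data sections have no term or sensitivity analysis for weighing method.

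The weight matters in three places:

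- **Entry:** "Those who lose at least 5% of initial body weight during Phase I (N=70) will be eligible to participate in Phase II" (Phase II Approach, Participants).
- **Stratum:** Randomization stratifies on Phase I loss, 5-10% versus 10% or more.
- **Phase II:** weight is the secondary outcome, and the Phase II baseline weight is the reference for each participant's maintenance goal.

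**The concern.** A percent loss computed from two scales contains the offset between them. For someone weighed in clinic at entry and by home-scale photo at week 16, that offset can move the result across 5% or across 10%. A person who has not qualified can then be admitted, one who has can be refused, and an admitted person can be put in the wrong stratum. If the method changes again between month 0 and a later Phase II visit, the offset appears as regain or continued loss that did not happen.

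A switch is a realistic prospect. The waiver section says in-person orientation was not possible because of COVID-19, while Data Safety Monitoring sets out symptom screening for participants who do come to the lab. Both modes are foreseen, over two cohorts, a 16-week Phase I and a 4-month Phase II. A wrong admission or refusal cannot be undone at analysis.

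**Working it through.** **Inputs from the plan.** Phase I N = 160, Phase II N = 70 and an expected 54% reaching the 5% loss (Overview). BMI 30-50 kg/m² (Inclusion/Exclusion Criteria). The plan has no figure for weighing error. Its own figure for the gate gives 0.54 × 160 = 86.4, so about 86 are expected to pass.

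**Assumptions, because the plan gives none.** Starting weight W of 85-115 kg; true percent loss normal with SD s of 3-6 points; scale error of 1 kg. BMI 30-50 at heights of 1.60-1.80 m (also assumed) gives 76.8-162 kg, so 85-115 kg lies inside the eligible range.

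**Step 1: from kilograms to points of loss.** If the second scale reads b kg higher than the first, apparent loss = true loss − 100·b/W.
- W = 85: 100/85 = 1.18 points per kg
- W = 100: 1.00
- W = 115: 100/115 = 0.87

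The gate for a 100 kg person is 5 kg, so a second scale reading 1 kg low lets a true 4% loss pass.

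**Step 2: centre the distribution on the plan's pass rate.** Mean = 5 + s·z(0.54), with z(0.54) = 0.100. For s = 3 the mean is 5.30; for s = 6 it is 5.60.

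**Step 3: independent errors, SD 1 kg, everyone switched to the photo route.** Observed loss = true loss + error of SD 100/W points. Simulated results:

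| W (kg) | s (points) | Passers who are true non-qualifiers | Of 70 | Their mean true loss |
|---|---|---|---|---|
| 85 | 3 | 10.7% | 7.5 | 4.3% |
| 85 | 6 | 5.6% | 3.9 | 4.3% |
| 100 | 4 | 7.1% | 5.0 | 4.4% |
| 100 | 6 | 4.8% | 3.4 | 4.4% |
| 115 | 3 | 8.1% | 5.7 | 4.5% |
| 115 | 6 | 4.2% | 2.9 | 4.5% |

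The range is 4-11%, or about 3-8 of 70. Wrongful refusals are about as many as wrongful admissions: at W = 100 and s = 4, about 6 of each among 160. Over the whole grid, 6-10% of correctly admitted participants fall in the wrong weight-loss stratum.

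**Step 4: scale by use.** The share is roughly proportional to the fraction who switch. At an illustrative 20%, 0.20 × (4.2% to 10.7%) = 0.8% to 2.1%, or about 0.6-1.5 of 70.

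**Step 5: Phase II weight comparison.** If weight change has an SD of 4-6 kg (assumed) and every participant carries 1 kg of added error, the standard error rises by √(16+1)/4 = 1.03 to √(36+1)/6 = 1.01, that is 1-3%.

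**The case against.** The strongest reply is that this is a fallback. It applies only when in-person contact is a health risk, and the photo is listed last of three methods, although the plan does not formally rank them. The plan permits a change of scale but does not require one. Someone weighed on the same home scale at both ends carries a constant offset that largely cancels. Phase I participants also submit daily weights to the website, and Phase II adds session weights and weekly phone reports; these could expose an abrupt shift, though the plan does not prescribe that check. All of this limits exposure and stands. It does not remove the gap.

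A reader might infer more than the documents support:

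- **Large gate errors.** If every participant switched and every second scale read 1 kg low, 5.7-14.9% of Phase I (9-24 of 160) would falsely pass; at 1 kg high, 5.8-15.5% would falsely fail. Participants' own scales would not share one bias, and nothing suggests universal switching. Independent errors are the relevant case.
- **A biased treatment comparison.** Nothing ties weighing method to arm. A wrong stratum weakens balance without invalidating the randomisation, and the primary outcome is measured by accelerometer.
- **No clothing or shoe rule for photos.** The general rules, "Participants will be measured wearing light, indoor clothing without shoes" in Phase I and "Participants will be measured wearing one layer of clothing without shoes" in Phase II, are not waived by the contingency text. What the photo route lacks is supervision and calibration.
- **Participants choosing a favourable reading.** They do learn of the 5% rule at consent and the photo is unobserved, but nothing in the documents shows that this would occur.

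**Conclusion.** The concern holds as a gap in the contingency plan. When the weighing method changes between two weights, an unverified scale difference enters the entry decision, the stratum and Phase II weight change. Under the assumptions shown, 4-11% of those passing would be true non-qualifiers at full use of the photo route, and proportionately fewer at lower use. Those wrongly admitted average a true loss of about 4.3-4.5%, so they differ little from people just above the line. What results is misclassification at entry and in the stratum, and a small loss of precision in a secondary outcome. The between-arm comparison is not biased, and the primary outcome is touched only through who is admitted. The text of the plan is clear. The size is uncertain, because scale error, the spread of percent loss, starting weights and photo use are not in the documents. The change is worth making because entry errors are irreversible and the better method is already in the plan.

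**What to change.** Amend the Weight paragraph of the contingency plan:

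1. Base the 5% gate and the weight-loss stratum on study-scale weights only: clinic scale, e-scale, or mailed scale checked with calibration weights on video. Do not use home-scale photos for eligibility. They can remain a fallback for later weights that would otherwise be missing.
2. Keep each participant on one method within a phase where possible.
3. Record the method with every weight, and repeat the weight analysis without photo or mixed-method weights.

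I would not require weighing on both methods at a forced switch. When the switch is from clinic to remote, the clinic contact this needs is what the emergency rules out.

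The cost is protocol wording, one data field and one sensitivity analysis, plus some more shipping of mailed scales already in the plan and a possible short delay to the gate weight. Videoconference ability is already an entry condition during emergencies (Inclusion/Exclusion Criteria), so the supervised weigh-in needs no new infrastructure.

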The goal of the present study is to establish whether delayed discounting is engaged in a WLM intervention that involves EFT, whether this engagement mediates adherence to PA recommendations, and whether environmental factors moderate this relationship. We will do this by testing TST-based mediational pathways in both a standard WLM intervention (Weight Loss Maintenance- Healthy Thinking: WLM-HT) and a

WLM intervention that explicitly seeks to engage DD through EFT (Weight Loss Maintenance+ Future Thinking: WLM+FT). Given that the stated focus of many WLM interventions is on selfregulation^{14,18} and the data linking DD to eating and exercise behaviors^{29,40}, it is reasonable to propose that this putative target is engaged in standard WLM interventions, although this hypothesis has not yet been empirically tested. At the same time, we recognize that there is tremendous variability in response to WLM interventions⁶, which suggests the need to more systematically engage putative targets such as DD to improve behavioral adherence and long-term outcomes. EFT is a promising strategy but has yet to be explored in WLM. Thus, testing of the DD mediational pathway within these two interventions will allow for both within- group examinations of the hypothesized mechanism of action as well as between-group comparisons of whether explicit engagement of DD results in greater behavioral adherence and improved WLM outcomes. It is hypothesized that 1) Compared to WLM-HT, WLM+FT will produce more engagement of DD and PA adherence as measured by EMA and accelerometry. 2) In both WLM-HT and WLM+FT, within-person mediational pathways will be found between participation in the intervention and PA and changes in delayed discounting on 2a) a daily basis (EMA) and 2b) over longer-time periods (1- and 3-month change predicting PA outcomes at 6 months). 3) Environmental context will moderate the mediational pathways in both interventions such that DD will be a stronger determinant of behavior in environments with more proximal costs than in environments with more proximal benefits.

Design, Procedures, Materials, and Methods.

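### The single stated power of 82.1% fits an arm comparison averaged over visits; it does not cover primary hypothesis 2b, the indirect effect through DD change, for which no power is given

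*Combined protocol and SAP*

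**What the plan says.** The Power paragraph (Justification of Sample Size / Data Analysis) states that "power is computed for an effect size (d) of 0.50", and then: "The computations assume an intraclass correlation (ICC) of 0.250 for the 4 time points clustered within each participant". It adds "The standard deviation is assumed to be the same in the two conditions" and "The criterion for significance (alpha) has been set at 0.05", with a two-tailed test. It concludes: "Given these assumptions, the study will have 82.1% power to yield a statistically significant result". It does not say which hypothesis the figure serves, whether d refers to DD or PA, whether d applies per visit or on average, or how many participants are analysed.

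The Analyses section then labels two hypotheses primary. The first is an arm comparison. On the second it says "we will test how the relationship between intervention condition and PA is mediated by change in DD over time", and part 2b uses DD change at 1 and 2 months to predict PA at 4 months. The Purpose / Introduction makes this part of the study goal: "whether this engagement mediates adherence to PA recommendations". (The introduction words 2b with months 1, 3 and 6. The Analyses wording is used here because it matches the Phase II visits at 0, 1, 2 and 4 months.) No power, effect size for the second path, or sample-size argument is given for any mediation test.

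**The concern.** An indirect effect is a product of two paths: condition to DD change, and DD change to PA. Both must be detected, and the first path as worded uses a change between visits, not an average over four of them. A power computed for an averaged arm difference therefore does not carry over.

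At stake is how a null is read. Beside a study-level 82.1%, a non-significant indirect effect could be taken as evidence that DD does not carry the effect of episodic future thinking on PA. If the true power for 2b is much lower, such a result says little either way.

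**Working it through.** **Inputs from the plan.** d = 0.50, ICC 0.25, 4 time points, equal SDs (set to 1), two-sided alpha 0.05, 70 randomised, 15% attrition. **Inferred or assumed.** 1:1 allocation; 70 × 0.85 = 59.5, so about 30 completers per arm.

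**Step 1: reproduce 82.1%.** The variance of a four-visit mean is (1 + 3 × 0.25)/4 = 0.4375. The noncentrality is 0.50/√(2 × 0.4375/30) = 2.93, and the noncentral t with 58 df gives 82.1%. Two other routes give the same figure: the mean of the three post-baseline visits adjusted for month 0, whose variance is (1 + 2 × 0.25)/3 − 0.25² = 0.4375, and a normal approximation with 29 per arm. All are arm main-effect tests.

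**Step 2: two readings of d.**
- Reading A: d = 0.50 at each post-baseline visit. This is consistent with 82.1% through the baseline-adjusted three-visit mean. The unadjusted four-visit mean would differ by only 0.50 × 3/4 = 0.375, giving 57.9%.
- Reading B: d = 0.50 is the four-visit average with no difference at month 0. The post-baseline difference is then 0.50 × 4/3 = 0.667.

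**Step 3: power of the arm-to-DD path** at 30 per arm, from the noncentral t with noncentrality d/√(2V/30):

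| DD mediator | Variance V | Reading A | Reading B |
|---|---|---|---|
| Raw change to one visit | 2(1 − 0.25) = 1.5 | 34.3% | 54.5% |
| Mean of month-1 and month-2 changes | (1 + 0.25)/2 + 1 − 2 × 0.25 = 1.125 | 43.5% | 66.8% |
| One visit, adjusted for month 0 | 1 − 0.25² = 0.9375 | 50.3% | 74.6% |
| Months 1–2 pooled, adjusted for month 0 | (1 + 0.25)/2 − 0.25² = 0.5625 | 71.8% | 92.3% |

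With all 70 analysed, reading A gives 39.1%, 49.4%, 56.7% and 78.5%. Under a joint-significance test, path-one power is a strict ceiling for the indirect effect. Under a Monte Carlo interval for the product it is approximate: simulations gave up to about 38% where path-one power was 34%.

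**Step 4: add the DD-to-PA path.** Its size is not in the documents, so a partial correlation of 0.3 is assumed. By Fisher's z with 60 participants, adjusting for arm: atanh(0.3) × √(60 − 1 − 3) = 0.3095 × 7.48 = 2.32, so power is Φ(2.32 − 1.96) ≈ 64%. Adjusting also for month-0 DD gives about 63%. The product of the two path powers approximates joint power:
- raw single visit, reading A: 0.343 × 0.64 ≈ 22%
- adjusted single visit, reading A: 0.503 × 0.63 ≈ 32%
- pooled and adjusted, reading A: 0.718 × 0.63 ≈ 45%
- pooled and adjusted, reading B: 0.923 × 0.63 ≈ 58%

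Simulation of the joint test agrees to within about three points. For partial correlations of 0.2, 0.4 and 0.5 under reading A, simulated joint power is about 11%, 29% and 34% (raw single visit), 16%, 44% and 48% (adjusted single visit), and 24%, 64% and 70% (pooled and adjusted).

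**The case against.** A reader might infer that 2b is capped at about 34% on the plan's own inputs. The documents do not support that. It needs three choices the plan does not make: d = 0.50 per post-baseline visit, an unadjusted difference to a single visit, and 30 analysed per arm. It also mixes effect models if 82.1% is traced to the unadjusted four-visit mean, because that per-visit effect gives 57.9% there. Speaking of change in DD makes a raw difference a natural reading, but the plan specifies mixed-effects mediation and leaves baseline handling and the joining of the two lags open. So 34% is the low end of a range.

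Nor does every combination fall below 82.1%. Under reading B, with the pooled, adjusted mediator and a partial correlation of 0.5, path-two power is about 98% and the product is 0.923 × 0.98 ≈ 90%. That needs the larger per-visit effect, a mediator the plan does not define, and a strong second path.

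Three further points stand. The printed figure is not an arithmetical error: it reproduces, and its description (two conditions, equal SDs) suits an arm comparison. The calculation covers only the between-arm form of 2b. Hypothesis 2 is also worded as within-person pathways in both arms, and 2a rests on daily EMA data; power for these cannot be computed from the documents. Finally, the plan does not say that a null indirect effect would be read as evidence against mediation. That risk comes from the study-level wording.

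What does not stand is that the gap is therefore harmless. A hypothesis labelled primary has no power statement, and the only figure printed is attributed to the study as a whole.

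**Conclusion.** The concern holds in limited form. The 82.1% matches an arm main effect averaged over visits and should not be read as the power for 2b. The ceiling for the between-arm indirect effect is about 34% to 72% if d = 0.50 applies at each post-baseline visit, and about 55% to 92% if it is a four-visit average with no baseline difference. At an assumed partial correlation of 0.3 for the second path, joint power runs from about 22% to just under 60%.

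These figures grant d = 0.50 on DD and rest on ICC 0.25, compound symmetry and about 30 completers per arm. The origin of the 82.1% is inferred from an exact match, not stated. The width of the range is itself part of the finding: the plan has not defined the 2b test closely enough to attach one power to it.

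**What to change.** **Power paragraph.** Tie the 82.1% to the hypothesis 1 arm comparison, and state the outcome, the meaning of d and the analysed N. Say that it does not cover hypothesis 2. Give the 2b range with its assumptions, including the assumed DD-to-PA path, and not a single cap. Say that power for 2a and for within-arm pathways was not calculated.

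**Primary hypothesis 2 paragraph.** Define the 2b mediator as the month-1 and month-2 DD values pooled and adjusted for month-0 DD. Report the indirect effect with its 95% interval, and state that a non-significant result is inconclusive. Compared with raw change to one visit, this mediator raises the arm-to-DD ceiling from 34% to 72% under reading A and from 55% to 92% under reading B. Pooling raw changes alone reaches only 43% under reading A, so most of the gain needs the baseline adjustment. The choice should be fixed before outcome data are examined.

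**Cost.** Wording only, using DD data already scheduled, with no extra enrolment. The printed power for hypothesis 2 becomes less favourable, and separate estimates at each lag become descriptive.
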